**STUDY PROTOCOL INCLUDING STATISTICAL ANALYSIS PLAN**

**OFFICIAL TITLE: Does Guanfacine Attenuate Stress-Induced Drinking?**

**BRIEF TITLE: Does Guanfacine Attenuate Stress-Induced Drinking? ([name], PI)**

**CLINICALTRIALS.GOV ID: NCT02164422**

**PROTOCOL DATE: March 21, 2021**

Identifying effective medications for the treatment of alcohol use disorders remains a high priority as problems associated with alcohol use continues to be major public health problem. One promising, yet relatively unexplored avenue for medication development for alcohol use are therapeutics that target stress-reactivity. Several lines of evidence suggest that stress is a primary mediator of alcohol use and relapse. Preclinical research demonstrates that noradrenergic pathways are involved in stress-induced consumption and reinstatement to alcohol, as well as alcohol-related reinforcement and withdrawal, and that their manipulation may be of potential therapeutic benefit for alcohol use.

Guanfacine is an alpha2a adrenergic receptor agonist known to attenuate stress-induced reinstatement to alcohol and other drugs of abuse in preclinical studies. Guanfacine rescues the prefrontal cortex from detrimental effects of stress and improves working memory, attention, and behavioral control. In a study evaluating 3mg/day guanfacine for smoking cessation, we demonstrated that guanfacine was well tolerated, attenuated the effects of stress on smoking, reduced smoking-related reinforcement, improved cognition, and significantly reduced smoking during a brief treatment phase.

#### STUDY OBJECTIVE

To conduct a Phase II human laboratory study evaluating the effect of guanfacine on alcohol consumption. Using a double-blind, placebo-controlled, dose-ranging parallel group design, we randomized non-treatment seeking adults with alcohol use disorders (DSM-IV dependence or abuse) to guanfacine (3mg/day, 1.5mg/day, or placebo) to evaluate whether guanfacine reduces alcohol self-administered in the laboratory. Following titration to steady state medication levels over a 3-week period, each subject will complete two laboratory sessions to evaluate drinking during a 2-hour alcohol self-administration paradigm.

#### STUDY DESIGN AND METHODS

This study was a double-blind, placebo controlled, parallel-group design, to compare immediate release guanfacine (1.5, 3.0mg/day) to placebo (0mg/day) in adults meeting criteria for DSM-IV alcohol use disorders. This study consisted of an intake session, a physical exam, and two laboratory sessions following titration to steady state levels. Ad-lib alcohol consumption was assessed during the 2-hour session. Doses designed to raise alcohol to 0.12 g/dL were provided. Following the medication taper, subjects were assessed for an additional two weeks. Primary outcome measures include mls consumed during the self-administration sessions, and secondarily, the frequency and severity of adverse events during the titration period.

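### The one named adverse-event outcome stops at the end of titration, so as written it counts nothing from the laboratory alcohol sessions, the taper or the two-week follow-up (low severity, cheap to improve)

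*Combined protocol and SAP*

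**What the plan says.** Study Design and Methods names two outcomes. The first is consumption: "Primary outcome measures include mls consumed during the self-administration sessions". The second, placed in a secondary position in the same sentence, is "the frequency and severity of adverse events during the titration period". No other section names an adverse-event outcome, a safety reporting period or an adverse-event analysis. Statistical Considerations gives a model for mls consumed and nothing else.

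The order of the study is stated twice. Study Objective says "Following titration to steady state medication levels over a 3-week period", and continues "each subject will complete two laboratory sessions to evaluate drinking during a 2-hour alcohol self-administration paradigm". Study Design and Methods speaks of "two laboratory sessions following titration to steady state levels". On alcohol exposure in those sessions it says "Doses designed to raise alcohol to 0.12 g/dL were provided". It then describes what came after: "Following the medication taper, subjects were assessed for an additional two weeks". It does not say what was assessed in those two weeks.

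**The concern.** The named outcome carries an explicit time window, and that window closes before the laboratory sessions begin. Those sessions are the only alcohol administration that the protocol itself schedules, and they take place once subjects are at steady-state medication. An adverse event in a session would not be counted in the named outcome. Nor would an event during the taper or the two weeks after it. A difference between arms that arose only in those periods would not appear in it.

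The Eligibility section lists a history of fainting or syncopal attacks among the exclusions specific to guanfacine. That shows only that the plan treats fainting as a concern with this drug. If a subject fainted in a session, the outcome as defined would not include it.

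What is at stake is how much the trial can say about tolerability. The stated hypothesis concerns alcohol consumption, and no safety hypothesis is given.

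**Working it through.** The plan states no figure that could be reproduced here, so the check sets the outcome window against the order of the study.

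| Period | Source | Length given | Inside the adverse-event window? |
|---|---|---|---|
| Titration | Study Objective | 3 weeks | Yes |
| Laboratory session 1 | Study Objective; Study Design and Methods | 2 hours of self-administration | No |
| Laboratory session 2 | as above | 2 hours of self-administration | No |
| Taper | Study Design and Methods | not stated | No |
| Post-taper assessment | Study Design and Methods | two weeks | No |

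1. *Could the titration period mean the whole time on medication?* Both sections place the laboratory sessions after titration, and Study Objective gives titration its own length of 3 weeks. The text does not support the wider reading.

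2. *Scheduled sessions inside the window:* 0 of 2 per subject.

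3. *Laboratory drinking time inside the window:* 2 sessions × 2 hours = up to 4 hours per subject, of which 0 hours are inside. This assumes one 2-hour paradigm per session, which is how both sections read. It is an upper limit on exposure time. Drinking was ad-lib, and 0.12 g/dL describes what the doses were designed to reach, not the levels attained.

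4. *Does another section supply a wider window?* No. The only other tolerability statement is in the introductory text, and it concerns an earlier smoking-cessation study.

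5. *Can the number or share of events left out be calculated?* No. That would need the sample size, event rates, session spacing and taper length, and none of these is given.

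The counts in steps 2 and 3 describe coverage. They are not effect sizes.

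**The case against.** The strongest reply is that nothing here is an error. A titration-period window is a coherent measure of tolerability and contradicts nothing else in the documents. It can also be defended on statistical grounds. The hypothesis expects less drinking on guanfacine, so alcohol intake in the sessions is a post-randomisation variable that should differ by arm. Adverse events there would mix the effect of the drug with the amount of alcohol taken, and a titration comparison avoids the scheduled laboratory alcohol. The documents do not give this rationale, but it is reasonable. It supports keeping the outcome, and it means that session events can only be described. It is not a reason to leave them out of the report.

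Several stronger readings are tempting, and the documents do not support them:

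- *Later events were not collected.* Defining an outcome does not limit what was recorded. Contact continued for two weeks after the taper, and the list of outcomes is introduced by a word that leaves room for others.
- *Most of the trial lies outside the window.* A reader might count the rows of the table above and infer this. The periods are very unequal: three weeks of titration against at most 4 hours of laboratory drinking, a taper of unknown length, and two weeks after the taper.
- *All drinking while on the drug is missed.* The plan says "we randomized non-treatment seeking adults with alcohol use disorders", and drinking outside the laboratory during titration is not ruled out. Only the scheduled laboratory exposure can be placed outside the window.
- *Alcohol with guanfacine raises the risk of fainting.* No section says so. The exclusion concerns the drug, and it applies equally during titration, where events are counted.

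**Conclusion.** The point holds as a low-severity improvement. The single named adverse-event outcome counts no event from the two laboratory sessions, the taper or the post-taper assessment. Coverage of scheduled laboratory alcohol is 0 of 2 sessions per subject. Confidence is high about what the window includes. It does not extend to any harm resulting from it, since the number of events affected is unknown and could be zero.

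The conclusion rests on reading the titration period as the 3-week phase that precedes the sessions, and on no wider adverse-event outcome being named in the documents. The primary analysis of mls consumed is unaffected, and no estimate, test or hypothesis changes.

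**What to change.** Keep the titration-period outcome as stated. Add one supplementary descriptive table of adverse-event frequency and severity by arm, from first dose to the end of the two-week post-taper assessment, split into titration, laboratory sessions, taper and follow-up. Beside session events, show the mls consumed in that session. Label the table as added later if data have already been seen. For any phase in which events were not recorded, state that as a limitation.

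The cost is one table if later events were recorded, or one sentence if they were not. The main drawback is interpretive: session events by arm partly reflect differences in alcohol intake. Showing mls consumed makes this visible but does not remove it, so no formal comparison between arms should be drawn from that part of the table.

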#### ELIGIBILITY

Minimum Age: 21 Years

Maximum Age: 65 Years

Sex: All

Gender Based:

Accepts Healthy Volunteers: Yes

Criteria:

Inclusion Criteria:

Age 21-65

Able to read and write English

Meets Diagnostic and Statistical Manual of Mental Disorders (DSM-IV) criteria for current (past 6 months) alcohol abuse or alcohol dependence

Exclusion Criteria:

Participants with any significant current medical conditions, seizures, delirium or hallucinations, or other unstable medical conditions including HIV

Current DSM-IV abuse or dependence on substances, other than alcohol abuse, alcohol dependence, or nicotine dependence

Women who are pregnant or nursing

Suicidal, homicidal or evidence of current (past 6-month) mental illness

Meet DSM-IV criteria for current (past-6 month) attention deficit hyperactivity disorder (ADHD)

Specific exclusions for administration of guanfacine not already specified include: EKG evidence at baseline screening of any clinically significant conduction abnormalities or arrhythmias; known intolerance for guanfacine or any alpha blocker; history of fainting, syncopal attacks, heart failure or myocardial infarction, or impaired liver as indicated by aspartate aminotransferase (AST), alanine aminotransferase (ALT) > 3x normal or renal function (estimated creatinine clearance <60 cc/min); treatment with any antihypertensive drug or any alpha-adrenergic blocker; use of any central nervous system (CNS) depressant (e.g., phenothiazines, barbiturates, benzodiazepines)

Subjects likely to exhibit clinically significant alcohol withdrawal during the study.

Individuals who are seeking treatment for drinking

#### STATISTICAL CONSIDERATIONS

PRIMARY HYPOTHESIS: During the laboratory component, 3mg/day guanfacine and 1.5mg/day guanfacine vs placebo will reduce alcohol consumption. Linear mixed models with medication condition, lab session, and time were used to evaluate mls consumed.

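### Does the primary hypothesis need a named deciding term and a one-or-both-doses rule, given that the title asks about stress-induced drinking?

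*Combined protocol and SAP*

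**What the plan says.** The title poses the question "Does Guanfacine Attenuate Stress-Induced Drinking". The background that follows it describes an earlier smoking study of guanfacine, which "attenuated the effects of stress on smoking, reduced smoking-related reinforcement, improved cognition, and significantly reduced smoking during a brief treatment phase". An effect on stress reactivity and an effect on consumption are thus listed there as separate results.

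The Study Objective is "to evaluate whether guanfacine reduces alcohol self-administered in the laboratory", with three arms, "guanfacine (3mg/day, 1.5mg/day, or placebo", and it says that "each subject will complete two laboratory sessions to evaluate drinking during a 2-hour alcohol self-administration paradigm". Study Design and Methods gives the endpoint: "Primary outcome measures include mls consumed during the self-administration sessions".

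Statistical Considerations has two sentences. The hypothesis is "3mg/day guanfacine and 1.5mg/day guanfacine vs placebo will reduce alcohol consumption". The method is "Linear mixed models with medication condition, lab session, and time were used to evaluate mls consumed". No interaction, contrast, alpha, sidedness, multiplicity method or dose rule is given, and nothing in the document says how the two sessions differ.

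**The concern.** Two choices appear to be open.

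**Which term decides.** The hypothesis suggests the medication effect averaged over sessions. If one session were a stress session, the title would suggest medication-by-session. An average effect does not show that stress-induced drinking is attenuated, and an effect confined to one session can be diluted in the average.

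**Which dose rule applies.** Two doses are set against placebo. The sentence could mean that both must win, that either may win, or that an overall medication test comes first. If only one dose works, the answer depends heavily on which of these is used.

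If such choices were made after the data were seen, a positive claim could not be told apart from a selected one.

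**Working it through.** The documents give no sample size, power, alpha or variance, so there is no stated figure to reproduce. The check compares the sections and then illustrates the size of each choice.

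**Inputs from the documents:** three arms, two sessions per subject, millilitres consumed as the endpoint, and a mixed model with medication, session and time.

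**Assumed, not in the documents:** two-sided 0.05 per contrast, equal allocation, equal variance in the two sessions, between-session correlation r of 0.3 to 0.7, and 80% power for an effect that exists (noncentrality 1.960 + 0.842 = 2.802). Success means significance in the direction of less drinking.

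**1. Sections side by side**

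| Section | Question |
|---|---|
| Title and background | Stress-induced drinking (rationale) |
| Study Objective | Drinking in the laboratory |
| Study Design and Methods | Millilitres consumed in the sessions |
| Statistical Considerations | Reduction in consumption, each dose against placebo |

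The three sections that define the trial agree. Only the title and rationale differ.

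**2. Deciding term**

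With unit variance per session, the session average has variance (1+r)/2, the session difference has variance 2(1−r), and the two are uncorrelated.

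- *Equal effect in both sessions.* The session difference is truly zero, so that term is significant in a given direction 2.5% of the time. This is the correct error rate for a different question.
- *Effect δ in one session only.* The average carries δ/2 and the difference carries δ. The ratio of noncentralities (difference over average) is √((1+r)/(1−r)). If the session term has 80% power, the average has power Φ(2.802/ratio − 1.960):

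| r | Ratio | Power of the average |
|---|---|---|
| 0.3 | 1.363 | 54% |
| 0.5 | 1.732 | 37% |
| 0.7 | 2.380 | 22% |

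These figures matter only if the sessions differ by stress, which the document does not say. Without that, even the favourable direction of the session term is undefined.

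**3. Dose rule, on the session average**

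The two contrasts share the placebo arm, so they correlate at 0.5. P(either) = p₁ + p₂ − P(both), with P(both) from the bivariate normal. The column for an overall 2-df test first comes from simulation with 15 to 50 per arm.

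| Truth | Either dose | Overall test first | Both doses |
|---|---|---|---|
| Neither works | 0.025 + 0.025 − 0.0046 = 4.5% | 2.1% | 0.5% |
| One works (80%) | 0.800 + 0.025 − 0.0247 = 80% | 75% | 2.5% |
| Both work (80% each) | 0.800 + 0.800 − 0.687 = 91% | 83% | 69% |

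The either-dose false-reduction rate moves only from 4.2% to 4.7% as allocation (doses to placebo) goes from 2:2:1 to 1:1:2. Counting significance in either direction, the equal-arm rate is 9.1%.

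**4. Price of formal adjustment**

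Dunnett at equal allocation has critical z 2.212 (two-sided p 0.027 per dose). A contrast with 80% unadjusted power falls to Φ(2.802 − 2.212) = 72%.

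**The case for a change.** The strongest case for a change is that the whole statistical plan is two sentences, with nothing blacked out there, and that closing the gap costs little. The smoking-study summary shows that the authors themselves separate stress attenuation from reduced use. The hypothesis is a prediction, not a success rule: with one effective dose, a positive trial is 80% likely under one reading and 2.5% under another. Without adjustment the either-dose reading exceeds a 2.5% one-sided error. If either of the two model terms could also carry the claim, the rate would be 1 − (1 − 0.0454)² = 8.9%.

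Part of this stands. The contrast, the dose rule, alpha and sidedness are not stated, so a reader cannot verify from this document which were used, and a session average does not answer the title.

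The rest is weaker. The 8.9% needs medication-by-session to be a route to the primary claim. No section names that interaction, and none says that either session is a stress session. The 80% against 2.5% comparison takes the two extreme rules and a pass/fail frame that the document does not set up, since it defines no trial success. Once each dose is reported in millilitres with its interval, a reader can apply either rule. Nor would new wording make the rule prospective: the past tense in Statistical Considerations suggests that the model has been fitted.

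**Conclusion.** The concern does not call for a change to the plan. It identifies missing detail that an analyst would fill sensibly: each dose against placebo, taken over the two sessions, which is what the objective, endpoint and hypothesis jointly describe. That analysis is sound for the stated hypothesis. Its false-reduction rate is about 4.5% if either dose may win unadjusted, 2.1% after an overall test, and 0.5% if both must win.

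Dunnett adjustment is the only change of method in play. It matters only under the ungated either-dose reading, and it would take a contrast from 80% to about 72% power. In a Phase II dose-ranging laboratory study that is a fair trade-off to leave to the authors.

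The mismatch with the title limits interpretation. It does not create a rival primary test. The report can say how the sessions differed and which contrast, dose rule and alpha were used, and should not draw a conclusion about stress-induced drinking from the session average.

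All figures rest on assumed 80% power, two-sided 0.05 and equal arms (except where allocation is varied). The one-session figures and the 8.9% rest further on the unstated premise that the sessions differ by stress. None of the figures describes the trial's actual power.

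### Is it a fault that the primary model of volume drunk has no term for the amount of alcohol offered to each subject?

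*Combined protocol and SAP*

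**What the plan says.** The section Statistical Considerations gives the whole analysis in one sentence: "Linear mixed models with medication condition, lab session, and time were used to evaluate mls consumed". It names no covariate for the amount offered, body weight, sex or baseline drinking.

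Study Design and Methods supplies the setting. The outcome is an absolute volume ("Primary outcome measures include mls consumed during the self-administration sessions"), drunk at will ("Ad-lib alcohol consumption was assessed during the 2-hour session"). On the amount, the only statement is "Doses designed to raise alcohol to 0.12 g/dL were provided". The comparison is between subjects: "This study was a double-blind, placebo controlled, parallel-group design".

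Study Objective names the three randomised arms ("guanfacine (3mg/day, 1.5mg/day, or placebo) to evaluate whether guanfacine reduces alcohol self-administered in the laboratory") and places the measurements after treatment has begun: "Following titration to steady state medication levels over a 3-week period, each subject will complete two laboratory sessions".

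**The concern.** A drink prepared to reach a given blood-alcohol level usually suggests an amount scaled to the person, and Eligibility admits both sexes with no weight limit. If a larger person was offered more and so drank more, part of the spread in volume drunk reflects what was offered and not the drug. In a parallel-group trial that spread goes into the standard error of each dose-versus-placebo contrast. Two sessions per subject reduce within-subject noise but leave it untouched.

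The amount must have been known when the drinks were prepared, so a covariate looks almost free. What would be at stake is precision, and hence power, for the medication main effect. A covariate that is constant within a subject does not sharpen a medication-by-session or medication-by-time term.

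**Working it through.** **Inputs.** From the documents: three arms, two sessions, volume drunk as outcome, and the three named model terms. The documents give no sample size, standard deviation, effect size, alpha, allocation ratio or dosing formula. There is therefore no planned figure to reproduce, and everything numerical below is assumed and shown as a range.

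**1. Validity.** With random allocation, an amount set independently of arm is balanced in expectation, so omitting it does not bias the contrast. A null simulation (equal arm means, coefficient of variation (CV) of the amount 20%, intake proportional to the amount) rejects 5.2% of the time unadjusted and 5.1% adjusted, at a nominal 5%.

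**2. Cost and break-even.** For one covariate in three arms with total size N, the expected variance ratio of an arm contrast, adjusted to unadjusted, is

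(1 - rho²) × (1 + 1/(N - 5)),

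where rho is the within-arm correlation between the covariate and subject-level volume drunk. It breaks even at rho² = 1/(N - 4).

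- N = 45: factor 1 + 1/40 = 1.025; standard error up 1.2% if rho = 0; break-even |rho| = √(1/41) = 0.16.
- N = 60: factor 1 + 1/55 = 1.018; standard error up 0.9%; break-even |rho| = √(1/56) = 0.13.
- N = 75: factor 1 + 1/70 = 1.014; standard error up 0.7%; break-even |rho| = √(1/71) = 0.12.

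The cost is small, but there is a gain only if rho exceeds these values.

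**3. What rho could be.** If volume drunk = amount × fraction drunk, with the two independent and CVs c and f, then rho² = c²/(c² + f² + c²f²).

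- c = 0.10, f = 0.7: 0.01/(0.01 + 0.49 + 0.0049) = 0.020. At N = 60 the variance ratio is 0.980 × 1.018 = 0.998, so essentially no gain.
- c = 0.25, f = 0.3: 0.0625/(0.0625 + 0.09 + 0.0056) = 0.395. At N = 60 the ratio is 0.605 × 1.018 = 0.616, about 38% less variance.
- c = 0 (same amount for all): rho² = 0 and no gain is possible.

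**4. Power under different intake patterns.** Simulation with three arms, high dose against placebo, two-sided 5%, 20,000 runs per cell, and mean fractions drunk of 0.35, 0.45 and 0.55. Entries are the change in power, in percentage points, from adding the covariate at 25 per arm. The Monte Carlo standard error is 0.1 to 0.25.

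| How intake depends on the amount | CV 10% | CV 15% | CV 20% | CV 25% |
|---|---|---|---|---|
| Proportional | +0.7 | +2.2 | +4.0 | +7.0 |
| Square root | -0.1 | 0.0 | +0.6 | +1.4 |
| Amount only caps intake | -0.7 | -0.5 | -0.6 | -0.3 |
| Volume fixed | -0.6 | -0.5 | -0.6 | -0.5 |

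A second square-root run reached -0.2 at CV 10%. Repetitions moved single entries by up to about half a point.

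With two sessions averaged per subject, which is closer to the design, the ranges are +0.6 to +6.4 (proportional), -0.4 to +1.2 (square root) and -0.6 to -0.2 (cap). At 15 per arm they are +0.3 to +6.7, -0.7 to +0.7 and -1.0 to -0.6, with -1.1 to -0.9 for fixed volume.

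**5. How strong the dependence must be.** If intake rises as the amount to the power b, the covariate pays at 25 per arm only when b exceeds about 0.65, 0.45, 0.35 and 0.3 at CVs of 10%, 15%, 20% and 25%. At 15 per arm the hurdle is higher: at CV 10% there is still a small loss at b = 0.85 (-0.2, standard error 0.17), and at CV 15% break-even is near 0.6.

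**6. What the text would have to establish.** A gain needs all of the following: the amount varied between subjects; it varied in the unit in which intake was measured; intake rose with it and was not merely capped by it; the rise was steep enough; the amount was set from pre-treatment measurements; and it was recorded. Study Design and Methods gives only the target level. If total volume was held constant and only the strength changed, the volume offered was the same for everyone. If the amount was worked out at the session, it was set after the 3-week titration and might itself be affected by treatment.

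**The case for a change.** The strongest reply is that the bet is lopsided. The downside is about half a point of power at 25 per arm and about one point at 15, while the upside reaches about 7 points. An amount tailored to the person is also the natural reading of a blood-level target in a mixed-sex sample. One sentence from the sponsor would settle whether it varied, and one covariate would then suffice.

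Two parts of this stand: the model has no such term, and a covariate fixed before treatment that predicts intake would have been a reasonable choice at the planning stage. The rest does not make a fault. The 7 points need strict proportionality together with a CV of 25%. The square-root and cap patterns are no less compatible with the text and give -0.7 to +1.4 at 25 per arm. Substituting weight and sex would mean two covariates, costing about 1.4 points at 25 per arm and 2.0 at 15 if neither is prognostic.

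Timing also matters. The document carries "PROTOCOL DATE: March 21, 2021" and reports the models in the past tense. A covariate added after unblinding is post hoc, so the primary model would stay as it is and the adjusted fit could only be a labelled sensitivity analysis.

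**Conclusion.** The concern does not hold. Leaving out the amount offered biases nothing and leaves the type I error at about 5%, so the stated model is a legitimate choice for a randomised comparison. Whether a covariate would have helped cannot be determined from the documents: at 25 per arm the change in power runs from -0.7 to +7.0 points, and its sign depends on how intake related to the amount, which is nowhere described. All of these magnitudes rest on assumed sample sizes, CVs and intake patterns. What remains is an optional preference about precision, with no error to correct and no stated result that would change.

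### Does the plan need to name an analysis set, given that drinking is first measured after a three-week titration?

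*Combined protocol and SAP*

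**What the plan says.** The analysis is described under Statistical Considerations in two sentences. The hypothesis is "During the laboratory component, 3mg/day guanfacine and 1.5mg/day guanfacine vs placebo will reduce alcohol consumption", and the model is "Linear mixed models with medication condition, lab session, and time were used to evaluate mls consumed". No section names an analysis set or says how a randomised subject without a laboratory session is handled.

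The timing comes from two other sections. Study Objective says of allocation: "we randomized non-treatment seeking adults with alcohol use disorders (DSM-IV dependence or abuse) to guanfacine (3mg/day, 1.5mg/day, or placebo". It then says: "Following titration to steady state medication levels over a 3-week period, each subject will complete two laboratory sessions". Study Design and Methods lists the visits: "This study consisted of an intake session, a physical exam, and two laboratory sessions following titration to steady state levels". No drinking session before titration is listed. The same section gives the outcomes: "Primary outcome measures include mls consumed during the self-administration sessions, and secondarily, the frequency and severity of adverse events during the titration period".

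**The concern.** Randomisation protects a comparison of everyone randomised. It gives less protection to a comparison of those who stayed through three weeks of blinded titration, because staying can depend on the assigned arm. Adverse events during titration are an outcome of this trial, so loss that differs between guanfacine and placebo is plausible. If those who left would also have drunk more, or less, than those who stayed, the medication contrast among the stayers is shifted, in an unknown direction. A reader of the statistical section cannot tell which subjects the estimate describes, or whether the plan's authors had considered the matter.

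Subjects with only one session are a separate matter. The mixed model keeps them by default, under missing at random and a correctly specified covariance. The gap concerns subjects with no session at all.

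**Working it through.** **1. Is the set really undetermined?** The outcome exists only in the two sessions after titration. A likelihood-based mixed model uses observed outcome rows and nothing else. A subject with no session has no row, and a subject with one or two sessions has some. The model sentence and the visit list together therefore fix the set: randomised subjects with at least one session, compared by arm. One step is inferred. The documents do not state outright that randomisation preceded titration, but titrating to blinded assigned doses implies it.

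**2. How large could the bias be?** The documents give no sample size, SD, alpha or loss rate, so there is no figure of the plan's to reproduce. Everything below is assumed and is for scale only:
- 30 per arm, and two-sided testing at 5%;
- outcome taken as the two-session mean, with between-session correlation 0.6;
- share p of an arm lost before session 1;
- correlation rho of 0.2 to 0.5 between drinking and a latent normal propensity to leave;
- units of the one-session SD, either sign.

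The shift in the stayers' mean in one arm is rho × φ(z_p)/(1 − p). The factor φ(z_p)/(1 − p) is:
- p = 5%: 0.1031/0.95 = 0.109
- p = 10%: 0.1755/0.90 = 0.195
- p = 20%: 0.2800/0.80 = 0.350

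The bias in the contrast is the difference between the two arms' shifts. The standard error is √0.8 × √(1/n1 + 1/n0), where 0.8 = (1 + 0.6)/2. Type I error comes from the non-central t distribution.

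| Loss, active vs placebo | Bias (SD), rho 0.2 / 0.5 | SE (SD) | Type I error, rho 0.2 / 0.5 |
|---|---|---|---|
| 10% vs 5% (27 vs 28.5) | 0.017 / 0.043 | 0.240 | 5.06% / 5.36% |
| 20% vs 5% (24 vs 28.5) | 0.048 / 0.121 | 0.248 | 5.42% / 7.65% |
| 10% vs 10%, same rho in both arms | 0 / 0 | 0.243 | 5% / 5% |
| 10% vs 10%, rho in one arm only | 0.039 / 0.097 | 0.243 | 5.28% / 6.79% |

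For 20% vs 5%, the type I error is 5.3% to 6.7% at 20 per arm and 5.6% to 8.6% at 40 per arm.

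**3. What does the worst case require?** The implied gap in drinking between leavers and stayers is rho × φ(z_p)/[p(1 − p)]. At rho = 0.5 this is 0.5 × 2.17 = 1.09 SD for 5% loss and 0.5 × 1.75 = 0.87 SD for 20% loss. The 7.65% therefore needs a fourfold difference in loss and leavers who differ from stayers by about one SD. rho also has to be read as a correlation with the latent propensity. The correlation with actually leaving is lower, 0.24 to 0.35 at rho = 0.5 for 5% to 20% loss.

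**4. What would naming the set change?** The added sentence would describe the set that the model already uses. The endpoint, model terms, subjects analysed and primary result would be the same before and after.

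**The case for a change.** The strongest case for acting is that the document is titled as a protocol including the statistical analysis plan, so the analysis set belongs in it. Limiting the hypothesis to the laboratory component says where the effect is measured, not which randomised subjects count. Saying that each subject will complete two sessions is an expectation about conduct, not a rule. The tolerability statement in the introduction, "we demonstrated that guanfacine was well tolerated", refers to an earlier smoking study. The remedy would be cheap: a sentence or two and a table by arm of subjects with zero, one and two sessions.

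Most of this stands as description. The set is not named, and bias is possible. Two parts do not carry through to a change in the plan.

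- The useful part of the remedy is the table of counts and reasons for loss. Those are results, and their absence from a plan is not a fault in the plan.
- A sensitivity analysis triggered by a numerical rule would add little. Take a rule of loss above 10% in any arm, or more than 5 percentage points between arms. At 30 per arm, 5 points is passed by a difference of two subjects. With identical true loss in all three arms, chance alone triggers the rule 62% of the time at 5% loss and 86% at 10%. Observed loss of exactly 10% in every arm does not pass the numerical limits, although equal loss related to drinking in one arm only can give a type I error of up to 6.8%.

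**Conclusion.** The statistical section omits the analysis set, and the estimate applies to randomised subjects who reached the laboratory. This is a gap that analysts fill sensibly: the outcome exists only at the two sessions, the model uses all observed sessions, and the hypothesis is already confined to the laboratory component. No wrong choice is shown, and stating the set would leave the analysis and its result unchanged.

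The size of any bias is unknown because the documents give no loss figures. Under the assumptions above, modest differential loss (10% vs 5%) leaves the type I error within about 0.4 percentage points of nominal. A materially higher error needs large differential loss together with leavers who drink very differently, or equal loss related to drinking in only one arm. The documents support none of these. Confidence is high that the omission exists. There is no basis for saying that it affected the result.
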